^a “Non-CR/non-PD” is preferred over “stable disease” for non-target disease since stable disease is increasingly used as an endpoint for assessment of efficacy in some trials; thus, assigning “stable disease” when no lesions can be measured is not advised.

B. Missing Assessments and Not-Evaluable Designation

When no imaging/measurement is done at all at a particular timepoint, the patient is not evaluable at that timepoint. If only a subset of lesion measurements are made at an assessment, usually the case is also considered not evaluable at that timepoint, unless a convincing argument can be made that the contribution of the individual missing lesion(s) would not change the assigned timepoint response. This would be most likely to happen in the case of PD. For example, if a patient had a baseline sum of 50 mm with three measured lesions and, during the study, only two lesions were assessed, but those gave a sum of 80 mm; the patient will have achieved PD status, regardless of the contribution of the missing lesion.

If one or more target lesions were not assessed either because the scan was not done or the scan could not be assessed because of poor image quality or obstructed view, the response for target lesions should be “unable to assess” since the patient is not evaluable. Similarly, if one or more non-target lesions are not assessed, the response for non-target lesions should be “unable to assess” except where there is clear progression. Overall response would be “unable to assess” if either the target response or the non-target response is “unable to assess,” except where this is clear evidence of progression as this equates with the case being not evaluable at that timepoint.

Table 3. Best Overall Response When Confirmation Is Required

Overall Response at First Timepoint	Overall Response at Subsequent Timepoint	Best Overall Response
CR	CR	CR
CR	PR	SD, PD, or PR ^a
CR	SD	SD, provided minimum duration for SD was met; otherwise, PD
CR	PD	SD, provided minimum duration for SD was met; otherwise, PD
CR	NE	SD, provided minimum duration for SD was met; otherwise, NE
PR	CR	PR
PR	PR	PR
PR	SD	SD
PR	PD	SD, provided minimum duration for SD was met; otherwise, PD
PR	NE	SD, provided minimum duration for SD was met; otherwise, NE
NE	NE	NE

CR = complete response; NE = not evaluable; PD = progressive disease; PR = partial response;
 SD = stable disease.

^a If a CR is truly met at the first timepoint, any disease seen at a subsequent timepoint, even disease meeting PR criteria relative to baseline, qualifies as PD at that point (since disease must have reappeared after CR). Best response would depend on whether the minimum duration for SD was met. However, sometimes CR may be claimed when subsequent scans suggest small lesions were likely still present and in fact the patient had PR, not CR, at the first timepoint. Under these circumstances, the original CR should be changed to PR and the best response is PR.

C. Special Notes on Response Assessment

When nodal disease is included in the sum of target lesions and the nodes decrease to “normal” size (<10 mm), they may still have a measurement reported on scans. This measurement should be recorded even though the nodes are normal in order not to overstate progression should it be based on increase in size of the nodes. As noted earlier, this means that patients with CR may not have a total sum of “zero” on the CRF.

Patients with a global deterioration of health status requiring discontinuation of treatment without objective evidence of disease progression at that time should be reported as “symptomatic deterioration.” Every effort should be made to document objective progression even after

discontinuation of treatment. Symptomatic deterioration is not a descriptor of an objective response; it is a reason for stopping study therapy. The objective response status of such patients is to be determined by evaluation of target and non-target disease as shown in Tables 1–3.

For equivocal findings of progression (e.g., very small and uncertain new lesions; cystic changes or necrosis in existing lesions), treatment may continue until the next scheduled assessment. If at the next scheduled assessment progression is confirmed, the date of progression should be the earlier date when progression was suspected.

In studies for which patients with advanced disease are eligible (i.e., primary disease still or partially present), the primary tumor should also be captured as a target or non-target lesion, as appropriate. This is to avoid an incorrect assessment of complete response if the primary tumor is still present but not evaluated as a target or non-target lesion.

Appendix 5 Immune-Related RECIST Criteria

Immune-related RECIST (irRECIST) is derived from RECIST 1.1 conventions (Eisenhauer et al, 2009). The implementation of irRECIST (Perrone, 2016) is identical to RECIST 1.1 until progressive disease (PD) is identified. Upon demonstration of PD per RECIST 1.1, patients may remain on study per Investigator discretion, assuming the patient remains clinically stable, as defined in the protocol. Patients that remain on study will have an imaging disease assessment performed at least 4 weeks after the initial PD is demonstrated in order to confirm PD.

EVALUATION OF LESIONS

1.1 Evaluation of Target Lesions

- Immune-related Complete Response (irCR): **Disappearance of all target lesions.** Any pathological lymph nodes (whether target or non-target) must have reduction in short axis to <10 mm.
- Immune-related Partial Response (irPR): At least a **30% decrease in the sum of diameters of target lesions** (i.e., Percentage Change in Tumor Burden), taking as reference the baseline sum diameters.
- Immune-related Progressive Disease (irPD): Same requirements for PD as standard RECIST 1.1, with exception that progressive disease must be confirmed. After demonstration of PD by standard RECIST 1.1 criteria, patients remain on study and are re-imaged after >4 weeks. Confirmation of target lesion PD is constituted by the following:
 - Sum of linear diameters (SLD) reaches PD threshold of $\geq 20\%$ increase from nadirOR
 - SLD remains $\geq 20\%$ increased above baseline (if already $\geq 20\%$ increased at initial PD)
- Immune-related Stable Disease (irSD): Neither sufficient shrinkage to qualify for irPR nor sufficient increase to qualify for irPD, taking as reference the smallest sum diameters while on study.

1.2 Special Notes on the Assessment of Target Lesions

Lymph Nodes

Lymph nodes merit special mention since they are normal anatomical structures which may be visible by imaging even if not involved by tumor. Pathological nodes which are defined as measurable and may be identified as target lesions must meet the criterion of **a short axis of ≥ 15 mm by CT scan.** Only the *short* axis of these nodes will contribute to the baseline sum. Nodes that have a short axis < 10 mm are considered non-pathological and should not be recorded or followed.

Target Lesions that Become “Too Small to Measure”

All lesions (nodal and non-nodal) recorded at baseline should have their actual measurements recorded at each subsequent evaluation, even when very small (e.g., 2 mm). If the radiologist is able to provide an actual measurement, that should be recorded, even if it is below 5 mm. However, when such a lesion becomes difficult to assign an exact measure to then:

- If it is the opinion of the radiologist that the lesion has likely disappeared, the measurement should be recorded as 0 mm.
- If the lesion is believed to be present and is faintly seen but too small to measure, a default value of 5 mm should be assigned (note: in case of a lymph node believed to be present and faintly seen but too small to measure, a default value of 5 mm should be assigned in this circumstance as well). This default value is derived from the 5 mm CT slice thickness (**but should not be changed with varying CT slice thickness**).

Target Lesions that Split or Coalesce on Treatment

When non-nodal lesions „fragment,” the longest diameters of the fragmented portions should be added together to calculate the target lesion sum. As lesions coalesce, a plane between them may be maintained that would aid in obtaining maximal diameter measurements of each individual lesion. If the lesions have truly coalesced such that they are no longer separable, the vector of the longest diameter in this instance should be the maximal longest diameter for the “coalesced lesion.”

1.3 Evaluation of Non-target Lesions

While some non-target lesions may actually be measurable, they need not be measured and instead should be assessed only qualitatively at the time points specified in the protocol.

- Immune-related Complete Response (irCR): Disappearance of all non-target lesions. All lymph nodes must be non-pathological in size (< 10 mm short axis).
- Immune-related Non-CR/Non-PD (ir-Non-CR/Non-PD): Persistence of one or more non-target lesion(s). This also includes non-target lesions that demonstrated unequivocal progression at the initial demonstration of PD but then stabilized or regressed on subsequent scans.
- Immune-related Progressive Disease (irPD): Unequivocal progression of existing non-target lesions on a disease assessment subsequent to initial demonstration of PD. Therefore, irPD by non-target lesions requires one of the following on a disease assessment >4 weeks after the initial demonstration of PD:
 - New unequivocal progression

OR

- Further unequivocal progression (if unequivocal progression present at initial PD)

1.4 New Lesions

Recording of New Target Lesions

The longest diameters of new non-nodal measurable lesions and short axes of new nodal measurable lesions will be recorded. They will be added into the sum of diameters of target lesions (i.e. incorporated into the total Tumor Burden) for this and all subsequent follow-up assessments.

In order to be selected as new measurable lesions (≤ 2 lesions per organ, ≤ 5 lesions total, per time point), new lesions must meet criteria as defined for baseline target lesion selection and meet the same minimum size requirements of 10 mm in long diameter and minimum 15 mm in short axis for new measurable lymph nodes. New measurable lesions shall be prioritized according to size, and the largest lesions shall be selected as new measured lesions.

Recording of New Non-Target Lesions

All new lesions not selected as new measurable lesions are considered new non-target lesions and are followed qualitatively. Only a massive and unequivocal progression of new non-measurable lesions leads to an overall assessment of irPD for the time point. Persisting new nonmeasurable lesions prevent irCR.

Progression by New Lesions

irPD by new lesions requires one of the following on a disease assessment >4 weeks after the initial demonstration of PD:

- New lesions appear
OR
- Additional new lesions appear
OR
- Prior new lesions grow (if new lesions were present at initial PD)

1.5 Confirmation of Progressive Disease

As described above, irPD requires that an initial demonstration of PD is confirmed in a subsequent disease assessment performed >4 weeks after the initial demonstration of PD. The above section describes what constitutes irPD with respect to Target Lesions, Non-target Lesions and New Lesions. For the sake of clarity, the presence of ALL of the following >4 weeks after initial PD means that PD IS NOT confirmed:

- Target lesions

- SLD is <20% increased from nadir
- Non-target lesions
 - No additional unequivocal progression from prior scan
- New lesions
 - No additional new lesions
 - Any prior new lesions are stable or shrinking (qualitatively)
- Clinical status
 - Patient remains clinically stable

RESPONSE CRITERIA

2.1 Time Point Response

A response assessment should occur at each time point specified in the protocol.

- **Immune-related Complete Response (irCR):** Complete disappearance of all tumor lesions (target and non-target), together with no new measurable or unmeasurable lesions, for at least 4 weeks from the date of documentation of irCR. All lymph nodes short axes must be < 10 mm.
- **Immune-related Partial Response (irPR):** The sum of the linear diameters (SLD) of all target lesions is measured and captured as the sum of diameters at baseline. At each subsequent tumor assessment, the SLD of all target lesions is calculated. A decrease in SLD, relative to baseline SLD, of 30% or greater is considered an irPR, in the absence of irCR or irPD.
- **Immune-related Stable Disease (irSD):** irSD is defined as the failure to meet criteria for irCR, irPR or irPD.
- **Immune-related Progressive Disease (irPD):** It is recommended for patients that are clinically stable to confirm PD at the following tumor assessment. Any of the following will constitute progressive disease:
 - Overall ir-response of irPD (per Table 1) after confirmation of PD with disease assessment >4 weeks after initial demonstration of PD
 - PD per RECIST 1.1 in a patient that is not clinically stable enough to remain on study for confirmation

Table 1: irRECIST 1.1 Definitions

Target Lesion Response per RECIST 1.1	Non-target Lesion Response	New Lesions	Overall ir-response
CR	CR	None OR completely resolved	irCR
PR	Ir-Non-CR/Non-PD	None OR stable/shrinking relative to first PD scan	irPR
SD	Ir-Non-CR/Non-PD	None OR stable/shrinking relative to first PD scan	irSD
PD (with confirmation)	Any	Any	irPD
Any	Presence of unequivocal progression \geq 4 weeks after initial PD scan	Any	irPD
Any	Any	Appearance of new lesions after initial PD scan	irPD

CR = complete response, PR = partial response, SD = stable disease, PD = progressive disease, ir= Immune-related

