Tumour assessment (CT or MRI)	For subjects who continue treatment post-confirmed progression at the investigator's discretion, tumour assessments should be performed relative to the date of first infusion per section 10 until durvalumab is stopped. For subjects who discontinue durvalumab following loss of clinical benefit , scans should be conducted according to local clinical practice and submitted for central review until a new treatment is started (these scans are optional).							

^a Can be collected by phone.

^b Patients with ongoing \geq grade 2 or serious AEs will continue to be followed until the event is resolved to baseline or deemed irreversible or clinically insignificant by the site investigator, or start of new therapy.

^c Free T3 and free T4 will only be measured if TSH is abnormal or if there is clinical suspicion of an endocrine related AE.

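### Appendix 5 has no route to irPD for a clinically stable patient who stops at first RECIST PD and is not scanned again, so irRECIST PFS, DOR and possibly CBR are biased upward

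*Combined protocol and SAP*

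**What the plan says.** **Routes to irPD.** Appendix 5, section 1.5, states that "irPD requires that an initial demonstration of PD is confirmed in a subsequent disease assessment performed >4 weeks after the initial demonstration of PD". Section 2.1 of the same appendix adds one alternative: "PD per RECIST 1.1 in a patient that is not clinically stable enough to remain on study for confirmation". It introduces both with softer wording: "It is recommended for patients that are clinically stable to confirm PD at the following tumor assessment".

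**Residual category.** Section 2.1 also says that "irSD is defined as the failure to meet criteria for irCR, irPR or irPD". Table 1 gives irSD only where the target lesions are themselves SD, and its target-lesion PD row covers confirmed PD only.

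**Who is re-imaged.** Appendix 5, section 1.1, assumes that "patients remain on study and are re-imaged after >4 weeks". The introduction to the appendix is conditional: "patients may remain on study per Investigator discretion", and "Patients that remain on study will have an imaging disease assessment performed at least 4 weeks after the initial PD is demonstrated". Section 9.2 makes treatment past progression discretionary and requires a newly signed consent. For patients who stop for loss of clinical benefit, the tumour assessment row of Appendix 3 says that "scans should be conducted according to local clinical practice and submitted for central review until a new treatment is started (these scans are optional".

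**Analysis.** Section 14.3 names irRECIST ORR, PFS, CBR and DOR as secondary endpoints and estimates them as for RECIST. PFS ends at progression or death and is otherwise censored at last follow-up. CBR counts CR, PR and SD by 24 weeks.

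**The concern.** A patient with documented RECIST PD who is clinically well, and who stops by choice or to start another therapy, may never have the confirming scan. Appendix 5 has no rule for a missing confirmation and, unlike Appendix 4, no not-evaluable category. Read literally, the definitions treat that patient as not having progressed.

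Section 14.3 includes irRECIST to capture delayed responses. A gap between RECIST and irRECIST results will therefore be read as delayed immune benefit. If part of that gap comes from scans that were never done, the reading is wrong, and always in the favourable direction.

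**Working it through.** **1. The plan's own figure.** The only design figure is the Simon minimax rule in section 14.2: 13 then 27 patients, stop at 0/13, promising at 4 or more of 27. P(promising) = Σ over x = 1..13 of Bin(x; 13, p) × P(Y ≥ 4 − x), with Y ~ Bin(14, p). This gives 0.0416 at p = 0.05 and 0.801 at p = 0.20, and a full search returns the same design. It concerns RECIST 1.1 ORR, so nothing below changes it. The plan states no figure for the irRECIST endpoints.

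**2. Tracing the patient through Appendix 5.** Stable, first RECIST PD, stops, no later evaluable scan:

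| Rule | Met? |
|---|---|
| Confirmed on an assessment more than 4 weeks later | No, there is no assessment |
| RECIST PD and too unstable to wait for confirmation | No, the patient is stable |
| Table 1, target-lesion PD row | No, it needs confirmation |
| Table 1, non-target and new-lesion irPD rows | No, they refer to findings after the initial PD scan |
| Section 1.5, PD not confirmed | No, it is defined by findings more than 4 weeks later |
| Section 2.1, residual irSD sentence | Yes (irPR instead if the sum is still at least 30% below baseline) |

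Text and table disagree on the label. Neither gives irPD.

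**3. PFS and DOR.** With no irPD date, the next possible event is death; otherwise the patient is censored.

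Illustration with assumed inputs (200,000 simulated patients):
- 8-weekly scans, as in section 10.3
- exponential and independent times to PD and death
- median time to PD 9, 16 or 26 weeks
- median OS 8.9 or 15 months (values within Table 1 of section 3.2)
- follow-up 52 to 130 weeks
- 10% to 40% of progressors affected
- 24-week PFS read at week 25

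Results for median time to PD of 16 weeks (range over the two OS values):

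| Share affected | 24-week irPFS, censored at last follow-up | 24-week irPFS, censored at the PD scan |
|---|---|---|
| 0% | 0.23–0.27 | 0.23–0.27 |
| 10% | 0.27–0.32 | 0.26–0.31 |
| 40% | 0.39–0.47 | 0.36–0.43 |

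At 40% affected, with censoring at last follow-up, median irPFS moves from 16 weeks to 19–24 weeks. Over all scenarios and both censoring readings, the rise in 24-week irPFS is 2 to 7 points at 10% affected and 11 to 26 points at 40%. DOR moves the same way but only through responders, about 0.20 × 27 = 5.4 patients at the target ORR.

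**4. CBR.** The ceiling per patient is 1/27 = 3.7 points. Who adds to the count depends on how SD by 24 weeks is read:
- *Any SD scan by week 24:* only a patient whose first PD is at the first scan adds. SD at week 8 and PD at week 16 already counts as benefit under RECIST.
- *Status at week 24:* only a patient whose first PD falls at about week 24 adds.

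Example from an assumed 8/27, with exact 90% limits (lower = Beta quantile 0.05 at x, n − x + 1; upper = Beta quantile 0.95 at x + 1, n − x):
- 8/27 = 29.6% (15.7–47.1)
- two added: 10/27 = 37.0% (21.7–54.7)
- four added: 12/27 = 44.4% (28.0–61.8)

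**The case against.** **Confirmation is only recommended, so unconfirmed PD may still count.** The list that follows that sentence says what constitutes irPD, and unconfirmed PD in a stable patient is not on it. If confirmation is optional, section 2.1 contradicts section 1.5, and a rule is needed anyway.

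**The irSD label is not settled.** This stands. The label rests on the residual sentence, which Table 1 does not support, and some patients would be irPR. It is safe to say that these patients are not irPD; it is not safe to say that all of them are irSD.

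**Few patients will fall in the gap.** This stands in part:
- Some who stop for loss of benefit will be unstable and meet the second route.
- Appendix 2 continues scans until confirmed PD after completion of treatment or a toxicity stop.
- Section 9.4 waives the end-of-treatment scan only if one was done in the previous 28 days.
- Section 13.1 allows progression follow-up off treatment.
- Sections 9.4 and 10.4 assign Appendix 3 to confirmed PD, while its title says loss of clinical benefit.

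These provisions narrow the gap without closing it. A stable patient who stops soon after the PD scan need not be imaged again.

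**Stronger readings that a reader might infer.** One is that such patients are common, that each adds 3.7 points to irRECIST CBR, and that 2 to 8 of them would inflate it by 7 to 30 points. The documents give no count, and patients already counted as benefiting add nothing. Another is that each patient removes a PFS event. Death from any cause remains an event and all patients are followed for survival, so the event is delayed or may be lost.

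**Conclusion.** The defect holds as a missing classification rule with a known direction of bias. Applied as written, Appendix 5 and section 14.3 count documented RECIST PD without a later scan as non-progression. irRECIST PFS and DOR are biased upward for affected patients. CBR may be, by no more than 3.7 points for each patient who newly counts.

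The size cannot be derived from the documents. The PFS figures rest on assumed PD times, an assumed affected share, and independence of progression and death. Confidence is high on the missing rule and the direction, and low on the magnitude. Only secondary endpoints are involved, so this should be corrected but does not threaten the trial's main conclusion.

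**What to change.** Add to Appendix 5, section 2.1, and as a row in Table 1: RECIST 1.1 PD with no evaluable tumour assessment at least 4 weeks later, for any reason, is classified as irPD and dated at the first PD scan. Only a later scan, taken before any new anticancer therapy, that fails to confirm PD can reverse this. Repeat the rule in section 14.3 so that irRECIST PFS, DOR and CBR use it. Use one interval throughout, since Appendix 5 has both at least 4 weeks and more than 4 weeks.

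The cost is a sentence and a table row. No scans are added and treatment does not change. The downside is that a few unproven pseudo-progressions will count as irPD and irRECIST results will be less favourable. A sensitivity analysis that censors these patients at the first PD scan would show the effect, reported with the number of patients involved.

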2.2 Best Overall Response: All Time Points

Best Overall Response and Date of Progression Using irRECIST 1.1 (irBOR): The investigator will be asked to provide all responses on study and date(s) of progression, if applicable, and the best overall response will be calculated based on the time point responses and tumor measurements provided by the investigator.
